11.1 Set of statistical analyses

The data analyses are set up differently depending on the analysis goal and analysis cohort.

First, the approach to comparing the bivalent and monovalent booster relative efficacy based on the analysis cohort consisting of both PLWH and PLWoH will be described. Analyses that fall under this category include:

1. Primary analyses I/II and III/IV (when applicable);
2. Secondary analyses I and II (when applicable);
3. Exploratory analysis I.

Second, the approach to comparing the bivalent and monovalent booster relative efficacy but restricted to PLWH or PLWoH will be described. Analyses that fall under this category include:

1. Secondary analyses III, IV and V;
2. Exploratory analysis II.

Lastly, the exploratory analyses assessing if the COVID-19 incidence after receiving a M6 booster (bivalent/movalent) or not receiving a M6 booster differed between PLWH with hybrid (Analysis Group 2-1) or vaccine-induced immunity (Analysis Group 1) will be described. Analyses that fall under this category include:

1. Exploratory analyses III, IV and V.

The following statistical approaches are employed when evaluating the bivalent vs. monovalent booster relative efficacy.

1. Estimation of $E_W[P(T(a) \leq t_0 | W)]$, $a = 0, 1$, $\theta^{\text{diff}}(t_0)$, $\theta^{\text{rr}}(t_0)$, using nonparametric methods.
2. Estimation of the same parameters as estimated in 1 above except using semiparametric Cox modeling with T being the study time. While this approach also provides estimates of β coefficients, they are not used for results so as to avoid complications in interpretations when also reporting results for β coefficients for the calendar-time Cox modeling noted next.
3. Cox proportional hazards modeling with failure time on the calendar time scale and exposure variable the booster indicator (bivalent vs. monovalent), for estimation of β coefficients (this analysis does not estimate marginalized cumulative failure time parameters).

11.2 Hypothesis tests

Each nonparametric method described above provides 95% confidence intervals about the parameters of interest as well as two-sided p-values for testing the following null hypotheses of interest (with t_0 fixed at the latest time point of interest):

$$(A \text{ dichotomous}) \quad H_0 : \theta^{\text{diff}}(t_0) = 0, \quad \theta^{\text{rr}}(t_0) = 1 \quad (2)$$

Each Cox modeling method provides two-sided p-values for testing the following null hypotheses of interest:

$$(A \text{ dichotomous}) \quad H_0 : \beta = 0 \quad (3)$$

A partial likelihood ratio test will be used for testing each of the Cox model null hypotheses.

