***Modifying the final phase of the study based on findings from interim analyses***

Interim analyses of the pre-Month 6 study data have provided new information related to some of the study’s main research questions and have informed modifications to the final phase of the study. Consistent with observations in HIV-negative populations, mRNA-1273 appears safe and well tolerated in PLWH. Reactions after vaccinations were largely mild, with few severe reactions (3%) and no life-threatening or fatal reactions. To date, adverse events in general have been overwhelmingly mild and only one serious adverse event (a case of angioedema) has been considered potentially related to the vaccine. The pre-Month 6 data also suggest that in our study population, participants with hybrid immunity (ie, immunity from both prior infection and vaccination) experienced a reduced incidence of symptomatic SARS-CoV-2 infections compared to participants with only vaccine-induced immunity. Specifically, PLWH and HIV-negative participants who had evidence of prior SARS-CoV-2 infection at baseline and received one dose of mRNA-1273 had an annual COVID-19 incidence rate of 2.2% and 1.5% respectively, compared to 7.1% and 5.8% among such groups without evidence of prior infection at baseline and received two doses of mRNA-1273. This reduction in SARS-CoV-2 incidence could be due to the combination of natural immunity and mRNA-1273 vaccination or due to natural immunity alone. In addition, serious COVID-19 has been very rare in our study population during the pre-Month 6 period, with only 9 cases identified to date, including 7 in PLWH and 2 in people who were HIV-negative. However, asymptomatic SARS-CoV-2 infections were more common than previously appreciated, representing 86% of pre-Month 6 cases. In addition, the data suggest that there are a significant number of likely persistent infections. Of the 1298 (9.3%) participants with at least

one SARS-CoV-2 positive NAAT, 5.6%, 1.8%, and 1.5% were persistently NAAT positive at  $\geq 25$ , 50, 100 days, respectively. Deep genome sequencing of the sequential samples will help determine if these are persistent infections or reinfections (likely both) and what proportion of infections have acquired mutations. The persistent/recurrent infections appear to be more common among the participants without prior SARS-CoV-2 infection, those with active tuberculosis, and PLWH who have low CD4 T-cell counts and/or HIV viremia.

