## 6 Statistical considerations

### 6.1 Summary of statistical design

The statistical design primarily aims to evaluate 1) in the pre-Month 6 stage, the relative risk of COVID-19 and severe COVID-19 between the PLWH vaccine-only immunity group who are SARS-CoV-2 negative at enrollment, and assigned to receive 2 doses of pre-Month 6 vaccinations, and the PLWH hybrid immunity group who are SARS-CoV-2 positive at enrollment and assigned to receive 1 dose of pre-Month 6 vaccination (i.e., co-primary objectives 1 and 2) and; 2) in the post-Month 6 stage the relative risk of COVID-19 and severe COVID-19 between the mRNA-1273 and mRNA-1273.222 randomized arms (i.e., co-primary objectives 3 and 4). In the pre-Month 6 stage, the evaluation considers follow-up after enrollment until the Month 6 dose; in the post-Month 6 stage, the evaluation considers follow-up after the Month 6 dose until the end of study.

Severe COVID-19 is included as a coprimary endpoint, which recognizes the importance of evaluating severe COVID-19 in PLWH. Given uncertainty in the rate of severe COVID-19 at the time of the primary analysis, an adaptive decision based on the treatment-blinded number of severe COVID-19 endpoints is made of whether to retain severe COVID-19 as a primary endpoint or to change it to a secondary endpoint. In addition, as secondary objectives of this trial, the relative risk of COVID-19 and severe COVID-19 will be evaluated in Groups 1 and 3 combined vs. Groups 2 and 4 combined, accounting for baseline HIV-1 serostatus.

For the pre-Month 6 stage, given that the analysis groups defined by HIV and SARS-CoV-2 statuses, and the number of vaccinations received are not randomized, and the assignment of individuals to study groups is known to participants and study staff, the study objectives are assessed using methods that adjust for measured potential confounder variables (see Section 6.4.3). For the post-Month 6 stage, because participants were randomized at baseline to the assignment of the two different Month 6 vaccinations within each of Groups 1-4, adjustment for potential confounder variables is only considered for the assessment of secondary objectives, not the primary objectives.

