These calculations are carried out assuming 5% annual dropout, 5% probability of missing any of the 3 doses, VE(COVID) of 63% between Month 0 and Month 6 in Group 1 (SARs-CoV-2 negative) and in Group 2, and 5% six-month COVID-19 incidence rate among unvaccinated PLWH SARs-CoV-2 negative individuals in the community. The assumption on VE(COVID) of 63% between Month 0 and Month 6 accounts for a possible reduced protection of the vaccine regimen in PLWH against the SARS-CoV-2 variant at the time of the trial conduct. The 5% six-month background incidence rate assumption was based on the observed 4.7%, 5.25%, and 10.38% placebo arm six-month incidence rates among baseline SARS-CoV-2 negative participants in, respectively, the AstraZeneca phase 3 (149), Novavax phase 2 (107), and Janssen ENSEMBLE phase 3 (28) trials restricted to South African study sites, and building in conservative margin given the availability of vaccines to potentially reduce transmission and infection in the region. The background SARS-CoV-2 (re-infection) incidence rate among unvaccinated PLWH SARS-CoV-2 positive individuals in the community is assumed to be half of that of unvaccinated PLWH SARS-CoV-2 negative individuals based on the reported protection of approximately 55% against the Omicron variant from previous SARS-CoV-2 infection in South Africa (150-152) and in other countries (153). The statistical power is calculated using an exact binomial test with a (two-sided) false positive error rate of 0.05.

**Table 6-2 Pre-Month 6 stage:** power to detect relative risk (Months 0-6) being different from 1.0 between Group 1 (n=4200) and Group 2 (n=8400).

True VE (0-6) of Group 1 (n=4200)	Relative Risk (Groups 1 vs. 2)	Total expected number of events M0-6	Power
60%	1.3	189	45%
	1.6	176	85%
	2.0	167	99%
70%	1.2	149	17%
	1.5	135	59%
	2.0	125	96%
70%	1/1.3	207	45%
75%	1/1.6	203	85%
80%	1/2.0	200	99%
75%	1/1.2	159	17%
80%	1/1.5	153	59%
85%	1/2.0	150	96%

**Post-Month 6 stage:** power to detect relative risk (Months 6.5-18) being different from 1.0 between mRNA-1273 vs. mRNA-1273.222 Month 6 vaccination (n=4000, 2000 vs. 2000),.

Annual incidence for mRNA-1273 Month 6 vaccination arm	Relative Risk (mRNA-1273 vs. mRNA-1273.222)	Total expected number of events M6.5-18	Power
3.5%	1.5	110	54%
	2.0	106	93%
3.0%	2.0	91	87%
	2.5	90	99%
2.5%	2.0	76	78%
	2.5	75	96%

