The relative risk (of COVID-19, severe COVID-19, SARS-CoV-2 infection, or SARS-CoV-2 asymptomatic infection) is defined as the incidence rate ratio between the 2 treatment groups in the pre-Month 6 stage or between the 2 treatment arms within a group in the post-Month 6 stage. When there are at least 7 severe COVID-19 endpoints at the primary analysis for a given relative risk assessment, both COVID-19 and severe COVID-19 are used as coprimary endpoints. Otherwise, severe COVID-19 is considered as a secondary endpoint. For the final analyses of the pre-Month 6 objectives, the incidence will be compared across groups by estimating the marginalized cumulative incidence of the endpoint overtime for each group, using a causal inference method that adjusts for potential confounders and accounts for right-censoring of failure times. Under causal assumptions, the marginalized cumulative incidence equals the causal cumulative incidence, interpreted as cumulative incidence if, hypothetically, the entire study population were assigned to the given group under consideration. Sensitivity analyses may also be conducted to account for unobserved confounding factors. For the final analyses of the post-Month 6 objectives, the RR between treatment arms within each group will also be estimated. The causal inference approach used for the pre-Month 6 stage analysis may also be applied for estimating the relative risk of each endpoint for the post-Month 6 dose objectives. More details will be described in the SAP. For analyses before the final analyses, the RR may be estimated from a Poisson regression analysis for both pre- and post-Month 6 stages. To assess potential time effects of vaccine efficacy, the Nelson-Aalen method will be used to plot the estimated cumulative incidence rates over time for the comparison groups. Additional analysis of RR by specified viral

strain categories may also be performed using competing risks failure time methods, as detailed in the SAP.

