7.1 Primary and secondary analyses comparing randomized bivalent vs. monovalent boost arms

For post-M6 follow-up in Part B of the study, the primary analysis is the comparison of COVID-19 risk between the monovalent and bivalent randomized arms, counting events starting 14 days after the Month 6 vaccination in the Randomized Month 6 (RM6) analysis cohort. When there are at least 7 severe COVID-19 cases, the same analysis will be repeated for the severe COVID-19 endpoint as a co-primary endpoint but without covariate adjustment due to the expected small number of severe COVID-19 endpoints. The secondary analysis involves the same comparison of COVID-19 risk and severe COVID-19 (if applicable), but counting events starting 1 day after the Month 6 vaccination in the RM6 analysis cohort. Both the primary and secondary analyses will only include participants who received the Month 6 vaccination in Version 6 under the study-group-stratified randomization scheme.

Two types of estimation procedures are used in each of the primary and secondary analyses. We consider estimation of hazard ratios using Cox proportional hazards regression, as well as estimation of absolute and relative differences in cumulative incidence of infection using methodology recently proposed by Westling et al. (2023).

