11.4.1 Primary analyses

Primary analysis I compares the COVE and CDC-based COVID-19 endpoints among participants randomized to a monovalent or bivalent M6 booster (RM6), counting event starting 13 days post M6 vaccination. To achieve this within a calendar-time-scale Cox regression framework, we consider the following time origin and associated analysis.

Let τ_0 denote the calendar time when the first RM6 participant completed the booster dose. For participant i , the time origin equals the number of days between 13 days after the participant's booster dose and τ_0 . At any calendar time t , the risk set consists of RM6 participants who are at least 14 days post the M6 booster. We consider the following Cox regression model:

$$\lambda_{ji}(t | A_i, W_i) = \lambda_{0j}(t) \exp \{ \beta A_i + \gamma^T W_i \} I(t > \tau_i^{D14}), \quad (4)$$

where $\lambda_{0j}(t)$ is a stratum-j-specific baseline hazard, τ_i^{D14} is Day 14 post M6 booster, $A_i = 1$ if participant i received a bivalent booster and $A_i = 0$ if a monovalent booster. When analyzing data under model (4), we will report $\exp(\beta)$ which measures the hazard ratio conditional on baseline covariates W when comparing bivalent to monovalent M6 booster.

The Cox regression will be conducted using the following stratification and covariate adjustment strategies:

- Stratification: the analysis will be stratified by 4 study groups and the geographic region (RSA or not). Therefore, a total of $4 \times 2 = 8$ strata will be considered.
- Covariate adjustment: the analysis will adjust for sex assigned at birth, history of TB, and a binary indicator of having had an infection during Part A of the study as defined in Section 7.1. The history of TB will not be adjusted in analysis restricting to PLWoH because of the small sample size.

Primary analysis II will be based on the time origin and stratification/covariate adjustment strategies as described above but restricted to the full per-protocol participants (FPP).

Primary analyses III and IV, when applicable, will be based on the same time origin as described above; however, no stratification or covariate adjustment will be conducted because of the expected small number of endpoints.

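### At the counts that make severe COVID-19 co-primary (7 events or more), the planned partial likelihood ratio test has an unreliable false-positive rate: about 6.5% to 12.5% at 7 events, and roughly 4% to 11% at the counts just above

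*SAP*

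**What the plan says.** The protocol sets the trigger in section 6.4.3: "When there are at least 7 severe COVID-19 endpoints at the primary analysis for a given relative risk assessment", severe COVID-19 stands beside COVID-19 as a coprimary endpoint; below that it is secondary. Protocol 6.1 makes the choice on the pooled count: "an adaptive decision based on the treatment-blinded number of severe COVID-19 endpoints is made". SAP 7.1 carries this into the post-Month 6 comparison: "When there are at least 7 severe COVID-19 cases, the same analysis will be repeated for the severe COVID-19 endpoint as a co-primary endpoint". Table 2 of the SAP lists the resulting tests as Primary analyses III (randomized Month 6 cohort) and IV (full per-protocol cohort).

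For these two analyses SAP 11.4.1 says "no stratification or covariate adjustment will be conducted because of the expected small number of endpoints", so arm is the only term in the Cox model. On testing, SAP 11.2 says "Each Cox modeling method provides two-sided p-values for testing the following null hypotheses of interest" and then "A partial likelihood ratio test will be used for testing each of the Cox model null hypotheses". No exact, permutation or other small-count test is given for the severe endpoint.

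SAP 12 reports estimates, 95% intervals and nominal p-values without multiplicity adjustment. It gives no numeric alpha.

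**The concern.** The 7-event rule lets the severe analysis start at a count where the chi-square approximation behind a likelihood ratio test is weakest. The SAP recognises that numbers will be small, since it drops strata and covariates for that reason, but it leaves the test unchanged. It also requires 20 events before any inference on COVID-19 itself (SAP 7.1), while allowing large-sample inference on severe disease at 7.

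At stake is the p-value printed beside a co-primary result on severe disease. At the trigger, a single case moving between arms separates an unremarkable split from one that a reader would call significant, and the reported p-value can be well below the exact one.

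**Working it through.** **Inputs.**
- Trigger of 7 events, pooled over arms (Protocol 6.4.3; SAP 7.1). Because it uses only the blinded total, the test can be judged conditional on the event count d.
- Arm-only, unstratified Cox model (SAP 11.4.1); two-sided partial likelihood ratio test (SAP 11.2).
- 1:1 allocation (Protocol 6.3), blocked within study group among those vaccinated under Version 6 (SAP 2).
- Reference level 5%: inferred from the 95% intervals (SAP 12) and the planning alpha (Protocol 6.3.1).

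**The plan's own figures.** The documents give no error rate for the severe endpoint. The nearest stated figures are the post-Month 6 powers for COVID-19 in Protocol Table 6-2. An exact conditional binomial test (null share 0.5, alternative share RR/(1+RR), at most 0.025 per tail) gives 54.1%, 92.9%, 87.4%, 98.7%, 78.1% and 96.2%, against stated values of 54%, 93%, 87%, 99%, 78% and 96%. All six rows reproduce.

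**Size at 7 events, balanced arms.** With an arm-only model and equal risk sets, d null events split as Binomial(d, 0.5). For x events in one arm,

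LR = 2[x ln(x/(d/2)) + (d−x) ln((d−x)/(d/2))], compared with 3.841.

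| Split | LR | LRT p | Exact two-sided p |
|---|---|---|---|
| 7-0 | 9.70 | 0.0018 | 2/128 = 0.0156 |
| 6-1 | 3.96 | 0.0465 | 2(1+7)/128 = 0.125 |
| 5-2 | 1.33 | 0.249 | not needed |

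The likelihood ratio test rejects at 7-0 and 6-1 in either direction, so its size is 2(1+7)/128 = 12.5%.

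**Other counts, balanced arms.**

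| Events | Size |
|---|---|
| 8 | 2(1+8)/256 = 7.0% |
| 9 | 2(1+9)/512 = 3.9% |
| 10 | 2(1+10+45)/1024 = 10.9% |
| 11 | 2(1+11+55)/2048 = 6.5% |
| 12 | 2(1+12+66)/4096 = 3.9% |
| 13 | 2(1+13+78+286)/8192 = 9.2% |
| 20 | 4.1% |

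**Sensitivity to balance.** The 6-1 split clears the critical value narrowly (3.96 against 3.84). If one arm's risk-set share lies outside about 0.494 to 0.506, one of the two 6-1 splits no longer rejects. At share 0.49 the two statistics are 3.77 and 4.17, and the size at 7 is 6.5%. The 8-2 split at 10 events is also on the edge (LR 3.855), and the size there is 6.1% at share 0.49.

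**Check by simulation.** A calendar-time Cox model with delayed entry, 4,000 participants and 7 null events (8,000 trials per scenario, Monte Carlo error about 0.4 points) rejected in 12.1% and 12.6% of trials under blocked randomization and in 10.3% under simple randomization.

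**Average over the counts that may occur.** The expected number of severe events is an assumption. Protocol 2.1 reports serious COVID-19 in the pre-Month 6 period "with only 9 cases identified to date". Taking about 14,000 people for half a year, and 4,000 people for about a year with a rough 0.97 for dropout, gives 9/(14,000 × 0.5) × 4,000 × 0.97 = 5.0. The table averages the size over a Poisson count, given at least 7 events.

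| Assumed mean | Chance of 7 or more | Average size, balanced | Average size, share 0.49 |
|---|---|---|---|
| 5 | 24% | 9.2% | 6.2% |
| 7 | 55% | 8.3% | 5.9% |
| 10 | 87% | 7.2% | 5.6% |
| 20 | near 100% | 5.4% | 5.5% |

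**After the change.** At 7 events with balance, the exact conditional binomial test rejects only at 7-0. Its size is 2/128 = 1.6%, and it stays at or below 5% at every count from 7 to 30. Its power at 7 events is (2/3)^7 + (1/3)^7 = 5.9% at RR 2.0 and (5/7)^7 + (2/7)^7 = 9.5% at RR 2.5.

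**The case against.** Several points on the other side stand.

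- A reader might take 12.5% as the size of this test in general. It is not. It belongs to exactly 7 events with nearly exact balance. Blocking aims at balance by study group, but dropout, censoring at outside vaccination and per-protocol exclusions can move the risk-set share by more than 0.6 points, and the size at 7 is then about 6.5%. At 9 and 12 events the test is below 5%.
- A reader might infer that the SAP dropped an exact test that the protocol had planned for severe disease. The documents do not support this. The sentence "The statistical power is calculated using an exact binomial test with a (two-sided) false positive error rate of 0.05" describes power calculations, and Protocol 6.3.1 says that those focus on the COVID-19 endpoint. Protocol 6.4.3 leaves the analysis details to the SAP.
- The forecast of 5 events is weak. It rests on an interim count of cases described as serious, carried into a later period. If it is right, the co-primary test is reached only about 24% of the time, and the overall chance of a false-positive severe result is about 0.24 × 0.092 = 2%.
- The SAP states no success rule, reports nominal p-values, and says the study is not meant to license a product (SAP 7). The unadjusted cumulative incidence contrast also gives its own interval and p-value.

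The last point explains the lack of multiplicity control. It does not make a single p-value correct: a 6-1 split would be printed as 0.0465 when the exact value is 0.125. The interval is a related gap, because the SAP does not name its type. If it is a Wald interval, a 6-1 split gives a hazard ratio interval of 6·exp(±1.96·√(1 + 1/6)), about 0.72 to 49.8, beside p = 0.0465. At 7-0 the likelihood ratio test remains defined but the Cox estimate is infinite.

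**Conclusion.** The concern holds as a matter of unreliable size at low counts, not a fixed inflation to 12.5%. At the trigger of 7 events the size is 12.5% with balanced risk sets and about 6.5% once the share lies slightly outside 0.494 to 0.506. From 8 to 13 events with balance it moves between 3.9% and 10.9%. Given that the analysis is reached, the average is about 9% (balanced) or 6% (share 0.49) if 5 events are expected, and it approaches 5% as the expected count rises to 20.

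This rests on near 1:1 risk sets, on 5% as the implied reference level, and, for the averages only, on an assumed expected count. The point estimate, the 7-event rule and the COVID-19 analyses are not affected.

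**What to change.** In SAP 11.2 and 11.4.1, for the severe endpoint only:

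- Replace the likelihood ratio p-value with an exact conditional binomial test (events by arm given the total, null share equal to the person-time share), or with a permutation log-rank test.
- Report the matching exact confidence interval for the rate ratio, so that test and interval agree and a 7-0 split still yields a finite bound on one side.
- Keep the 7-event rule, and state that at 7 events with balanced arms only a 7-0 split can reach p<0.05.

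The same text should cover Secondary analysis II, which SAP 11.4.2 also leaves unstratified and unadjusted.

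The cost is a few lines of SAP wording and code, with no new data. The downside is conservatism at some counts: 1.6% size at 7 events, with power of about 6% at RR 2.0 and 9.5% at RR 2.5. That shows how little 7 events can establish under any valid test.
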